PROJECT TITLE:

Well Child Care Clinical Practice Redesign: A Parent Coach-Led Model of Care for Young Children.
Phase 2: Cluster RCT

PRINCIPAL INVESTIGATOR:

[name], MBA
Associate Professor of Pediatrics, Seattle Children's
[contact]
[contact]

[name], MPH (UCLA PI)
Professor of Pediatrics, UCLA
[contact]
[contact]

Clinical Trial Registration: [clinicaltrials.gov, NCT03797898](https://clinicaltrials.gov/ct2/show/NCT03797898)

Contents

1. Objectives	3
2. Background.....	3
3. Study Endpoints	4
4. Drugs, Devices and Biologics	5
5. Procedures Involved	5
6. Data and Specimen Banking	9
7. Sharing of Results.....	10
8. Study Timelines	10
9. Study Population	10
10. Number of Subjects.....	12
11. Withdrawal of Subjects	12
12. Risks to Subjects.....	13
13. Potential Benefits to Subjects.....	13
14. Data Analysis/Management	13
15. Confidentiality.....	14
16. Provisions to Monitor Data to Ensure the Safety of Subjects.....	15
17. Use of Social Media.....	15
18. Research Related Injury.....	15
19. Recruitment Methods	15
20. Consent/Assent Process	17
21. Process to Document Consent in Writing.....	20
22. HIPAA Authorization and RCW Criteria.....	21
23. Payments/Costs to Subjects	23
24. Setting	23
25. Resources Available	23
26. Coordinating Center Procedures	24
27. Good Clinical Practice	24

1. Objectives

1.1. Purpose, specific aims, or objectives:

Purpose:

Conduct a cluster Randomized Controlled Trial (RCT) of a newly designed model of Well-Child Care (WCC) (Phase 2)

Specific aims:

Aim 1: Measure the effect of PARENT on the receipt of nationally-recommended WCC services and parent experiences of care.

Aim 2: Determine the effects of PARENT on WCC, urgent care, and ED utilization, and on net costs.

Aim 3: Examine the effect of PARENT on clinician time allocation for WCC and urgent care visits.

Aim 4: Assess the effect of PARENT on parent-focused outcomes in an exploratory analysis.

1.2. Hypotheses to be tested:

H1: PARENT will improve receipt of WCC services and parent experiences of care

H2a: PARENT will result in improved up-to-date rates for WCC visits and reduced ED utilization

H2b: In a cost/cost-offset analysis, we will demonstrate that direct intervention costs of PARENT are offset by net reductions in ED utilization.

H3: Clinicians will shift time from providing routine WCC services in well-visits to chronic disease management and urgent care.

H4: PARENT will result in improved parental mental health parenting self-efficacy, and positive behaviors.

2. Background

2.1. Relevant prior experience and gaps in current knowledge:

Well-Child Care (WCC) visits for child preventive care during the first three years of life are critical because they may be the only opportunity before a child reaches preschool to identify and address important social, developmental, behavioral, and health issues that could have significant impact and long-lasting effects on children's lives as adults. Despite its potential, multiple studies have demonstrated that pediatric providers fail to provide all recommended preventive and developmental services at these visits and that most parents leave the visit with unaddressed psychosocial, developmental, and behavioral concerns. Further, these missed opportunities are more pronounced for children in low-income families.

A critical problem is that the structure of WCC in the U.S. cannot support the vast array of WCC needs of families. Key structural problems include (a) reliance on clinicians (pediatricians, family physicians, or nurse practitioners) for basic, routine WCC services, (b) limitation to a 15-minute face-to-face clinician-directed WCC visit for the wide array of education and guidance services in WCC, and (c) lack of a systematic, patient-driven method for visit customization to meet families' needs. These structural problems contribute to the wide variations in processes of care and preventive care outcomes, resulting in poorer quality of WCC and perhaps worse health outcomes, particularly for children in low-income communities.

To address the gaps in current WCC this study introduces a new model of care to meet the needs of children in low-income communities: Parent-focused Redesign for Encounters, Newborns to Toddlers (PARENT). PARENT is a team-based approach to care using a health educator ("Parent Coach") to provide the bulk of WCC services, address specific needs faced by families in low-income communities, and decrease reliance on the clinician as the primary provider of WCC services. The Parent Coach provides anticipatory guidance, psychosocial screening/referral, and developmental and behavioral surveillance, screening, and guidance at each WCC visit, and is supported by parent-focused pre-visit screening and visit prioritization, a brief, problem-focused clinician encounter for a physical exam and any concerns that require a clinician's attention, and an automated text message parent reminder and education service for periodic, age-specific messages to reinforce key health-related information recommended by Bright Futures national guidelines.

To assess the efficacy off PARENT we will conduct a cluster randomized controlled trial (RCT). The study will be conducted in partnership with 10 clinics.

There are 2 major phases to this study. In Phase 1 (IRB ID: STUDY00000413), we used a Community Engagement & Intervention Implementation process that has been successful in previous studies to guide the intervention adaptation process, Parent Coach training, practice workflow, and intervention implementation in the practices. In Phase 2 (this protocol), we will conduct a cluster RCT of PARENT to determine its effects on quality, utilization, and clinician efficiency, and its cost/cost-offset. Our community partners include two federally-qualified health centers (FQHC). FQHC #1 has 4 clinics participating in the study and FQHC #2 has 6 clinics participating in the study. The total number of clinics participating in the study is 10 clinics randomized at the clinic level to intervention or control condition. The intervention clinics will implement PARENT for all well-visits through age 2 years at their clinical site, and the control clinics will continue usual care (clinician directed well-visit). 1,000 families will be enrolled at infant age \leq 12 months and remain in the study for a period of 12 months. Parents will complete a survey at baseline and at 6 and 12-months post enrollment.

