5.1. Study design:⁸

Our community partners are two federally-qualified health centers (FQHC). FQHC #1 is located in the Tacoma area in Washington and the FQHC #2 is located in the San Fernando/Santa Clarita areas in Los Angeles, CA. FQHC #1 has 4 clinics participating in the study and FQHC #2 has 6 clinics participating in the study. The total number of clinics participating in the study is 10. The cluster randomization was conducted at the end of 2017 by the study statistician. The clinics were placed in blocks by FQHC, location and size and the assignment to control or intervention was done using a computer-generated random allocation. Below are the cluster-randomized assignments, stratified by block and clinic size:

Block	FQHC #1	Assignment
1	Eastside Lakewood	Intervention Control
2	Parkland Spanaway	Control Intervention

Block	FQHC #2	Assignment
1	Canoga Park Van Nuys	Control Intervention
2	Pacoima San Fernando	Intervention Control
3	Santa Clarita Valencia	Intervention Control

The five clinics randomized to intervention will implement the newly adapted model of well child check-up visits for children ages 0-3. The five clinics randomized to control will continue to use the same services that the clinics provide--their usual check-up visit as their typical clinician-led visit (well-visit time slots vary by practice).

Parent/legal guardians will receive the same services offered by these clinics for their child's health care whether they participate in this study or not.

Components of the newly designed model of WCC:

The PARENT intervention was adapted during the Project Working Group meetings in partnership with the two FQHCs (Phase 1: IRB ID: STUDY00000413).

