- **Parent Coach at each visit.** The Parent Coach is a Spanish/English-bilingual trained health educator hired by the respective FQHC who received seven weeks of training. The training consisted of self-directed learning based on *Bright Futures Guidelines, Third Edition*, relationship building with community organizations near each clinical site; mock visits; and pediatrician-observed visits with feedback at the practices. The Parent Coach will be available at the intervention clinics to serve as the primary provider of anticipatory guidance, psychosocial screening and referral, and developmental/behavioral guidance and screening at each check-up visit. They will talk to parents about any concerns parents might have about feeding, sleeping, parenting, safety, or other issues. The parent coach will use an adapted version of the *Bright Futures Previsit Questionnaire, Third Edition* for each well-child care visit to guide the visits with the parent. They will document their visit in the child's Electronic Health Record.
- **Well Child Help Line.** The Parent Coach will be available to answer parents' preventive care-related questions, conduct parent follow-up calls and visit reminders during business hours.
- **HealthyText Messages.** Parents will be offered the text messaging service at study enrollment and research staff will process the enrollment by providing the parent's cell phone #, child's DOB and language preference (English/Spanish). The library of text messages (English and Spanish) were adapted from Healthy-TXT, a text messaging service (Healthy-TXT, LLC, Chicago, IL), to the needs of the FQHCs. If parent choose to sign up, they will receive text messages each week focused on age-appropriate anticipatory guidance, health education, and reminders for WCC visits. Most messages include a link to an educational website (e.g., healthychildren.org) with a video or written information on that specific topic, or the message may include the clinic's telephone number for visit scheduling, the parent coach number or other information (e.g., poison control hotline). At any time, parents will be able to text STOP to end the service.

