5.2. Research procedures:⁹

Intervention and Control clinics: Parents/legal guardians checking in for a WCC visit or a visit in between for an infant ≤12 months will be approached by research staff. Research staff will obtain a schedule of WCC visit prior to visiting the clinic. The schedule will include date, type of WCC visit, language, MRN, and child's age in weeks or months, parent name, parent phone number, and home address.

Parent/ legal guardians will be approached while waiting for their WCC visit or by phone if research staff are unable to approach in-person.

Clinic flyer procedure:

Clinics will have flyers on display about the study as a method for alerting parents to the possibility of being approached by research staff. Parents may take a flyer from the clinic to initiate communication with study staff to determine eligibility, learn more about the study, review the information sheet, and give verbal consent.

Clinic recruitment procedure:

Research staff will let the clinic staff and front desk staff know when arriving and verify the schedule. The front desk staff will let parents/legal guardians know that someone is at the clinic to talk to them about the research study. If parent/legal guardian agrees to be approached, the front desk staff will let the research staff know.

Research staff will explain the study, screen for eligibility (they will be asked some questions), provide the parental permission and consent form, and obtain consent. When possible, parents/legal guardians will be given the opportunity to discuss the study in a private room.

Research staff will conduct the baseline survey after screening and obtaining consent while parent/legal guardian is waiting for their WCC visit in the waiting area. We will assign IDs to all screened parents/legal guardians but will conduct the survey only with those wanting to participate and if they are eligible. If the survey is not completed during the waiting room time period, we will ask parent/legal guardian if it is possible to complete the survey at the end of their WCC visit or by phone the same day or any other day but not later than 14 days from date of enrollment.

Phone call recruitment procedure:

When research staff are limited from recruitment on-site, clinic sites will be informed of pre-screened visits that are anticipated to be eligible for enrollment.

CHC and NEVHC sites:

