We will collect information on the number of people approached, the number of people who agreed to participate and the number of people who refused to participate and the reasons for their refusal.

We will collect contact information from the enrolled parent/legal guardian and spouse/partner (home and cell phone, email) to telephone them to complete the baseline survey, if needed. The information will be verified at each subsequent contact for the follow up surveys at 6-month and 12-months from date of enrollment. We will also ask parents to provide contact information for three relatives/friends who will always know their whereabouts. Because this study population frequently changes phone numbers, we will also ask participants to provide any social media handles, if they are willing, so that the study team can direct message them. Direct messaging will be utilized to get updated phone numbers or schedule a phone conversation and no other purposes. Additionally, to support retention we will contact participants by cell phone and email at 3- and 9-month time points to remind them of their study participation as well as confirm their contact information has not changed. Furthermore, we will send participating families a card for their baby's first birthday and for New Years from the research team to encourage engagement, remind them of their participation, and support follow-up survey retention.

The research staff will ask parents/legal guardians questions about their experiences in getting care so that we can compare the two types of well-child care.

We will conduct three waves of survey data (baseline, 6-month and 12-month) collection and chart review at the end:

- Baseline Survey (at enrollment): Experienced research staff will be responsible for data collection. Upon enrollment, parents will participate in a 35-minute survey to collect baseline demographic data on the infant, parent, and household and child's medical history.

- 6-Month Survey (participant retention survey by phone): Research staff will conduct a 15-minute phone survey at 6-months post-enrollment to aid in participant retention. The 6-month survey will update the child's medical history, household changes, and healthcare utilization (e.g., ED utilization).

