7.1. Plan to share results with subjects/others:¹⁸

The results of the evaluation will be shared with participants using a flyer. The results will be presented only in aggregate form and with data that is de-identified. We will not put any data in the child's medical record

8. Study Timelines

8.1. Duration of an individual subject's participation in the study:

12 months

8.2. Duration anticipated to enroll all study subjects:

12 months

8.3. Estimated date for the investigators to complete this study:

June 2021

9. Study Population¹⁹

9.1. Inclusion criteria for each subject population (e.g., patients, parents, providers):

Parent/legal guardian-Child dyad attending well child check-up visits or visits in between for a newborn to 12-month.

Parent is English or Spanish proficient

For multiple gestations, one infant will be randomly selected as the index child. Infants with special health care needs will not be excluded from the study, since these children generally need the same recommended preventive care services.

9.2. Exclusion criteria for each subject population:

More than one child attending WCC

Legal guardian of child is under 18 years of age

Parents who are employed by the CHC/NEVHC

Either member of the dyad previously enrolled

Sick-visit

Parents/legal guardian planning not to continue receiving well child care services at this clinic for their child in the next 12 months

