the fact that randomization is done at the clinic level. The outcome may be subject to transformation prior to fitting the model if non-normality is observed. The analysis will include intervention status as the main independent variable, adjusted for baseline covariates and other confounding factors. We will also test possible interaction effects between intervention and these covariates. All other outcome variables to measure experiences of care and receipt of other nationally-recommended WCC services are regarded as secondary. Each outcome will be analyzed using linear or generalized linear mixed effects models depending upon data distributions, with a similar setting as described above for anticipatory guidance.

Specific Aim 2a: Intervention effects on healthcare utilization (ER visits, hospitalizations, urgent care visits, regional center/early intervention, maternal mental health, support groups (e.g., breastfeeding, parenting classes), dentist, case management/social services) will be assessed using generalized linear mixed effects models for binary or count data with a similar setup as outlined for Aim 1. The model will include random effects to capture data clustering within clinic and the primary independent variable is intervention status. The analysis will be adjusted for any baseline child, parent, or household characteristics that are significantly different between control and intervention groups. We will also test interaction effects between intervention and the covariates.

Specific Aim 2b: Cost/cost-offset Analysis. We will conduct our analysis from the perspectives of the “social planner”⁸⁰ and of the payer (e.g., health plan or medical group), and consider intervention costs (direct and indirect) and cost offsets.

Specific Aim 4: We will utilize the same approach as described for Specific Aims 1 and 2a; i.e., linear or generalized linear mixed effects models, depending on the distribution of the outcome variables.

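### Baseline may follow PARENT exposure for some intervention families, and the adjustment rules do not exclude covariates that PARENT could already have changed

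*Combined protocol and SAP*

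**What the plan says.** **Delivery.** Section 2.1: "The intervention clinics will implement PARENT for all well-visits through age 2 years at their clinical site". Section 5.1 adds that "Parent/legal guardians will receive the same services offered by these clinics for their child's health care whether they participate in this study or not". Among the listed components, only the text messages are tied to joining the study: "Parents will be offered the text messaging service at study enrollment".

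**Entry.** Under section 9.1 an infant may enrol at any age from newborn to 12 months.

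**Baseline survey.** Section 5.2 intends it for the waiting area before the visit. If unfinished, it may be completed "at the end of their WCC visit or by phone the same day or any other day but not later than 14 days" from enrolment. Its described content is "baseline demographic data on the infant, parent, and household and child's medical history". The 6-month survey then updates medical history, household changes and utilisation, including ED use. The instruments for WCC services, care experience and parent outcomes are described only for the 12-month survey.

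**Adjustment.** In section 14.1, the Aim 1 model is "adjusted for baseline covariates and other confounding factors", with no list. Aim 2a adjusts for whichever child, parent or household characteristics at baseline differ significantly between arms. Aim 4 follows the approach of Aims 1 and 2a. Nothing in the plan records earlier coach visits, or whether the survey came before or after the index visit.

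**The concern.** A baseline covariate is safe to adjust for when treatment cannot have altered it. Here an older infant at an intervention clinic may already have had coach visits before enrolling, while a control infant of the same age has had usual care. Even an infant enrolled at a first visit may be surveyed after meeting the coach.

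If PARENT has already moved a covariate, conditioning on it takes the covariate's share of the effect out of the estimate, or adds to it, depending on sign. Prior ED use is the clearest case. If PARENT lowers ED use, then among families with equal prior use those in the PARENT arm carry the higher underlying risk, and adjustment pulls the ED effect toward zero.

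The Aim 2a rule aggravates this, because a variable PARENT has shifted is more likely to pass a significance screen than one it has not. ED visits are an endpoint (section 3.1), part of H2a and H2b, and one of the two outcomes behind the power calculation (section 10.4).

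**Working it through.** **1. The plan's own figure.** Section 10.4 gives 75 evaluable per site, 20% dropout and 10 sites. 75 / 0.80 = 93.75, rounded up to 94; 94 x 10 = 940. This reproduces, and the present point does not change it. The 80% power cannot be reproduced, because the pilot mean, SD and ED rates are not given.

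**2. Reference effect, back-calculated.** With ICC 0.01, the design effect is 1 + 74 x 0.01 = 1.74. Effective n per arm = 375 / 1.74 = 215.5. The difference detectable with 80% power is (1.960 + 0.842) x sqrt(2 / 215.5) = 0.270 SD (normal approximation; 0.308 SD with t on 8 df).

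**3. Effect of adjusting for a shifted covariate.** Let D12 be the true 12-month effect, D0 the shift PARENT has already caused in the covariate, and b the covariate's adjusted slope on the outcome. Then

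adjusted effect = D12 - b x D0, and share retained = 1 - b x f, with f = D0 / D12.

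The values of b and f are assumptions:

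| b | f | Retained | Power (from 80%) |
|---|---|---|---|
| any | 0 | 100% | 80% |
| 0.1 | 0.5 | 95% | 76% |
| 0.3 | 0.5 | 85% | 66% |
| 0.5 | 0.5 | 75% | 56% |
| 0.5 | 1 | 50% | 29% |

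The power column holds the standard error fixed, so it ignores any precision gained by adjusting. Simulation of 10 clinics x 75 (1,500 runs per setting) agrees with the formula: 0.227 against 0.229 for b = 0.3, f = 0.5, and 0.133 against 0.135 for b = 0.5, f = 1. With f = 0 the adjusted estimate was 0.266-0.269. The unadjusted difference stayed at 0.266-0.272 throughout. Loss arises only when the covariate was itself changed.

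**4. How many families could be exposed.** The documents do not say. As an upper illustration, assume PARENT running throughout and enrolment spread equally over visits at 0, 1, 2, 4, 6, 9 and 12 months. Then 6/7 = 86% have had an earlier visit, and mean prior exposure is 34/7 = 4.9 months. If every family enrolled at a first visit, the share with an earlier visit would be 0%.

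**5. Illustration for 2 or more ED visits.** Assumed: control rate 0.6-1.0 ED visits per year, rate ratio 0.5-0.7, gamma frailty variance 1-2, enrolment ages as in step 4; 12 scenarios of 400,000 infants. The model is logistic with arm and age, without and then with prior ED count, and the risk difference is standardised.
- PARENT affects prior ED use: the risk difference shrinks by roughly 13-33%. In one scenario near the top of the range it goes from -6.6 to -4.5 points, and 1 - 4.5/6.6 = 32%.
- PARENT does not affect prior ED use: the change is about 0%.

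**6. The Aim 2a screen.** Under the same assumptions with 940 families, prior ED count would differ significantly between arms in about 45-99% of trials. This uses an individual-level test that ignores clustering; a test respecting the 10 clinics would select it less often.

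**The case against.** The strongest case against is that exposure before enrolment and a vulnerable covariate are both inferred.

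- **Whole-arm contamination.** A reader might infer that the intervention arm's baseline is already treated. The documents do not support that. They give no date on which PARENT started; they say only that "The cluster randomization was conducted at the end of 2017 by the study statistician". An infant at a first visit whose parent is surveyed in the waiting room, the default, is untreated. What stands: sections 6.1 and 19.1 show enrolment both before March 2020 and during the pandemic. If PARENT was live for the early families, older infants recruited later at those clinics could have had coach visits.
- **Covariate content.** Demographics cannot plausibly be changed by coaching, and no baseline measure of anticipatory guidance or care experience is described. The Aim 1 primary model is therefore exposed mainly through its unlisted factors. Prior ED use is not named as a baseline item or covariate. That the 6-month survey updates utilisation suggests an earlier measurement but does not prove it, and the instruments are not in the text.
- **Direction.** Bias toward no effect is not general. If coach screening raises recorded problems and these predict ED use, adjustment would exaggerate the reduction.
- **Selection and estimand.** Section 9.2 excludes families "planning not to continue receiving well child care services at this clinic". A reader might infer that this removes families who disliked PARENT. The criterion applies to both arms, and nothing in the documents shows differential exclusion. In a clinic-level redesign analysed by assigned group, coach visits before enrolment belong to the assigned condition, so the estimand need not be renamed.

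What survives is that the plan has no safeguard, and that the Aim 2a rule works in the wrong direction.

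**Conclusion.** The point holds in limited form. Baseline may be post-exposure for an unknown share of intervention families, and section 14.1 neither lists covariates nor restricts them to ones PARENT cannot change. Aim 2a is the most vulnerable, because its rule is stated and tends to pick shifted variables. Aims 1 and 4 are at risk through open-ended adjustment.

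The 13-33% shrinkage is an illustration. It rests on assumed ED rates, rate ratios, frailty, visit ages and PARENT running throughout, and on prior ED count being collected and adjusted for. It is about zero if prior use is unaffected. No comparable figure can be given for anticipatory guidance, since no baseline measure of it is described. The defect is cheap to repair and should be repaired before analysis.

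**What to change.** **Section 14.1.** Replace Aim 2a's significance-based selection, and the open-ended adjustment in Aims 1 and 4, with one prespecified set that PARENT cannot change: infant age at enrolment, sex, birth history, parent age, education and language. Add the randomisation blocks where 10 clinics allow. With five blocks and one treatment term, 10 - 5 - 1 = 4 clinic-level degrees of freedom remain, against 8 without blocks. Move medical history, past utilisation and any other covariate PARENT could have altered to a sensitivity analysis.

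**Section 5.2.** Keep the post-visit and telephone fallback, since removing it would risk missing baseline data. Record whether each survey preceded the coach visit.

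**Chart review.** Count well-visits at the clinic before enrolment in both arms. Report a sensitivity analysis in infants with no earlier well-visit there. The count should be reported, not adjusted for, because H2a expects PARENT to alter visit attendance.

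**Cost.** The changes are wording, one survey-timing field and one extra count from a review already planned. Some precision is lost by leaving medical history and past use out of the main models, and the ICC of 0.01 in section 10.4 leans partly on covariate adjustment. The first-visit subset is small: under the equal-spread assumption, 750/7 = 107 evaluable infants, about 11 per clinic. It should be read as an estimate with its interval. N stays at 940.
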